8.1.1 Screening

Screening will be performed by the treating physician in every cardiac arrest patient at the moment of ROSC.

8.1.2 Follow Up Period

Clinical data, mentioned above, will be collected at 90 days after inclusion by interrogation of the clinical data system (Primuz).

8.2 Detailed Study Assessments

8.2.1 Laboratory Testings

First arterial lactate and pH, venous creatinine and troponin T level.

8.2.2 Safety Assessments

Registration of contrast dye volume (for both CT and ICA), total radiation dose.

9 Interventions/Treatment

9.1 Treatments Administered

Standard of care for the treatment of cardiac arrest survivors will be administered.

9.2 Product/Device Characteristics

ECG-less Cardiac software is an FDA-approved cardiac scan mode that acquires cardiac images without the need of a patient-attached ECG monitor. ECG-less Cardiac essentially utilizes existing CT system scan technology. The system uses a wide detector coverage of 160mm to provide full heart coverage and a fast gantry speed of 0.23 seconds per rotation to perform imaging in a single cardiac cycle. An estimate of the heart rhythm has to be provided, which is often readily available because emergency patients are already monitored. Based on the heart rhythm the scanner simulates an ECG signal. This simulated ECG signal provides virtual gating of the scan. The acquisition can be performed during a full heart cycle or three-quarters or half cycle, depending on how fast the heart rhythm is. The existing cardiac software options of SmartPhase (automated phase selection) and SnapShot Freeze 2 (optimized volume registration) amplify the quality of the images and correct for motion.

Patients are scanned using a Revolution Apex Elite system (GE Healthcare, Waukesha, WI -USA). We use a hyperdrive pulmonary CT angiography (523mm/s with 0.28s/rotation gantry speed). After a short delay of a few seconds (5-12 sec), allowing the contrast to leave the pulmonary circulation, and enter the aorta and coronary arteries, a coronary CT angiography is performed within the same contrast bolus. No extra contrast is given to acquire the cardiac images. No intravenous beta-blocker nor sublingual nitroglycerin is administered.

The total added exam time (assessing heart rhythm, preparing the scan parameters, the delay time and the acquisition itself) is about one to two minutes. The dose-length product (DLP) of the ECG-less cardiac scan depends on the duration of the scan time that is chosen. The average DLP is between 150 and 200 mGy.cm. The diagnostic reference level (DRL) as set by the Federal Agency for Nuclear Control (FANC) for a coronary CT angiography is 300 mGy.cm.

The combined pulmonary CT angiography and ECG-less cardiac scan can be used to diagnose all the pathologies that can be assessed on a conventional pulmonary CT angiography scan (including, but not limited to, pneumonia, pleural fluid, pulmonary embolism, pulmonary infarct, pulmonary mass, pneumothorax, pericardial fluid, etc.) and provides extra diagnostic information about coronary artery disease.

10 Data Collection and Management

10.1 Monitoring

The investigator must make all trial documentation and related records available in case a monitoring visit is requested. Also in case of regulatory inspections all trial documentation should be made available to the inspector(s). All participant data must be handled and treated confidentially.

10.2 Data Collection

An Electronic Data Capture system "RedCap" will be used for data collection. Trial data will be entered within reasonable time after the subject underwent the necessary investigations. Corrections/modifications will be automatically tracked by an audit trail detailing date and time of the correction and the name of person performing the correction.

10.3 Database Management and Quality Control

Degree of coronary stenosis is divided into 3 categories (0, <50%, ≥50%) for every coronary segment. Angiographic and CT images are respectively evaluated by the consensus of two interventional cardiologists (ICA) and two interventional radiologists (CCTA), blinded for clinical data. In case of discrepant results between the two readers of the same imaging modality, a third reader will provide the deciding assessment.

The final conclusion on whether or not the cause of the cardiac arrest is related to the CAD, will be made by the interventional cardiologist performing the ICA, taking into account the clinical context, ECG findings, angiographic data and intracoronary imaging in case of doubt.

The level of agreement on the grade of coronary stenosis between CCTA and ICA will be assessed with the Weighted Kappa coefficient.

11 Safety Monitoring and Reporting

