6.1 Primary Objectives

Investigate the feasibility and diagnostic accuracy of ECG-less gated CCTA in cardiac arrest survivors without STEMI, by means of agreement with ICA.

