6.3 Endpoints

Primary endpoint

- Percentage of patients correctly classified to coronary artery disease as the cause of cardiac arrest after the CT scan.

Secondary endpoints

- level of agreement between CCTA and ICA based evaluation of the degree of coronary stenosis.
- Feasibility: data on coronary stenosis based on ECG-less CCTA cannot be provided or is incompletely provided.
- Reasons for failure of complete CCTA reporting.
- Clinical outcomes at 90 days.

7 Research Methods

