7.2 Study Population

7.2.1 *Inclusion Criteria*

- Adults (≥ 18 years) with sustained return of spontaneous circulation (ROSC) following in/out-of-hospital cardiac arrest.
- Informed consent from patient or representative obtained before invasive coronary angiography.

7.2.2 *Exclusion Criteria*

- Patients on VA-ECMO
- ACS STEMI or STEMI "equivalent"
 - New left/right bundle branch block
 - ST segment depression in leads V1-V3, when the terminal T wave is positive and concomitant ST-segment elevation $\geq 0,5$ mm recorded in leads V7-V9 (posterior MI)
 - ST-segment elevation in V7-V9 (posterior MI) or V3R-V4R (RV MI)
- ACS NSTEMI with persistent ST depression despite optimal therapy, suggesting ongoing myocardial ischemia, with indication for an urgent ICA according to the treating physician.
- Hemodynamic/electrical instability precluding CT imaging (as perceived by the treating physician)
- Life-threatening arrhythmia potentially caused by acute myocardial ischemia
- Absolute contraindications to iodinated contrast
- Patients with a known non-cardiac cause of cardiac arrest (e.g., traumatic brain injury, overt hemorrhage, asphyxia/severe hypoxia due to known lung disease, trauma, severe

metabolic/electrolyte derangement, or intoxication) as perceived by the treating physician, where chest CT is considered unnecessary.

- Known or likely pregnancy or lactation
- Severe bleeding issue (as perceived by the treating physician) precluding heparin administration during radial access coronary angiography.
- Prior coronary intervention (stent implantation/CABG).
- CT findings indicating a condition that precludes coronary angiography in the short term.
- Patients with end-of-life care pathways.
- Participation in another intervention study interfering with the research questions in OPEN CCT Arrest.

7.2.3 *Contraception / Pregnancy Avoidance Measures*

Pregnant women will be excluded.

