8.1 Schedule of Activities

Chest CT scan (as early as possible) + CT brain (+ CT abdomen if perceived indicated by the treating physician) Pulmonary embolism/aortic dissection protocol ECG-less gated CCTA (1)	Standard of care Study-specific
Invasive coronary angiography (<24 hours after CT scan)	Standard of care
Registration of baseline characteristics at admission (2)	Standard of care
Registration of study related parameters (3)	Study specific
Assessment of 90 days outcome (4)	Study-specific
Assessment of agreement between ECG-less CCTA and ICA (5)	Study-specific

ECG-less gated CCTA

ECG-less Cardiac software is an FDA-approved cardiac scan mode that acquires cardiac images without the need of a patient-attached ECG monitor. ECG-less Cardiac essentially utilizes existing CT system scan technology. The system uses a wide detector coverage of 160mm to provide full heart coverage and a fast gantry speed of 0.23 seconds per rotation to perform imaging in a single cardiac cycle. An estimate of the heart rhythm has to be provided, which is often readily available because emergency patients are already monitored. Based on the heart rhythm the scanner simulates an ECG signal. This simulated ECG signal provides virtual gating of the scan. The acquisition can be performed during a full heart cycle or three-quarters or half cycle, depending on how fast the heart rhythm is. The existing cardiac software options of SmartPhase (automated phase selection) and SnapShot Freeze 2 (optimized volume registration) amplify the quality of the images and correct for motion.

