- Time-to-diagnosis of ACS as a cause of cardiac arrest
- Time-to-diagnosis of a non-cardiac cause of cardiac arrest
 - o Pulmonary embolism
 - o Intracranial hemorrhage
 - o Acute aortic dissection
 - o Other
- Feasibility (patients meeting inclusion criteria where ECG-less CCTA with sufficient quality was obtained)

(2) Outcome at 90 days

- Survival (Y/N)
- severe neurologic deficit (≥ 3) (Y/N)
- Median peak troponin release
- Median length of ICU stay (days)
- Median duration of catecholamine support (days)
- Median peak SAPS II score
- Rehospitalization for heart failure (Y/N)
- Acute kidney injury (Y/N)
- Need for renal replacement therapy (Y/N)
- ISTH major bleeding event
- Ischemic stroke
- Need for mechanical circulatory support (MCS)
- Treatment with Dual Antiplatelet Therapy (DAPT)
- LV function on 90 days ambulatory follow-up visit

(3) Assessment of agreement between CCTA and ICA

Degree of coronary stenosis is divided into 3 categories (0, <50%, ≥50%) for every coronary segment. Angiographic and CT images are respectively evaluated by the consensus of two interventional cardiologists (ICA) and two interventional radiologists (CCTA), blinded for clinical data. In case of discrepant results between the two readers of the same imaging modality, a third reader will provide the deciding assessment.

The level of agreement will be assessed with the Weighted Kappa coefficient.

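### The verdict that appears to define a correct classification comes from the one cardiologist performing the ICA after the CT, and the protocol neither masks that operator to the CCTA coronary read nor locks the CT-based classification

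*Protocol*

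**What the plan says.** Protocol section 6.3 gives the primary endpoint as "Percentage of patients correctly classified to coronary artery disease as the cause of cardiac arrest after the CT scan". It does not say against what the classification is judged correct.

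Section 10.3 is the only place that assigns a decision on the cause of the arrest: "The final conclusion on whether or not the cause of the cardiac arrest is related to the CAD, will be made by the interventional cardiologist" who performs the ICA. The decision is reached "by the interventional cardiologist performing the ICA, taking into account the clinical context, ECG findings, angiographic data and intracoronary imaging in case of doubt". CCTA is not on that list of inputs, and it is not excluded.

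The schedule in section 8.1 puts the ICA after the CT, within 24 hours. Section 7.2.2 excludes patients with "CT findings indicating a condition that precludes coronary angiography in the short term", so at least some CT findings are known and acted on before the ICA.

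Sections 8.1 and 10.3 also describe paired readers for each modality, with a third reader if they differ. On the CT side these are "two interventional radiologists (CCTA), blinded for clinical data". Their task is to grade stenosis per segment, and the named analysis is that "The level of agreement on the grade of coronary stenosis between CCTA and ICA will be assessed with the Weighted Kappa coefficient". That analysis is a secondary endpoint.

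**The concern.** A percentage correctly classified means something only against a reference that does not depend on the test being assessed. Here the natural reference is one person's judgement, formed after the test under study has been done and possibly reported. If that person knows the CCTA coronary read, some verdicts may follow it. Agreement because the CT was right then cannot be separated from agreement because the CT was known. The same problem arises in reverse if the CT-based classification can be completed or revised once the ICA result is known.

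The safeguards also sit in the wrong place. The stenosis grades behind the secondary kappa have two readers, blinding and a deciding reader. The cause verdict, which is the more judgemental of the two and lies behind the primary endpoint, has one operator who is expressly told to use the clinical picture.

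**Working it through.** **Reading the sections together**

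1. Section 6.3 needs a reference and names none. Section 10.3 supplies the only cause verdict. Section 8.1 also registers whether a culprit lesion was found and the time to a diagnosis of ACS, but names no other adjudicator. That the operator's verdict is the reference is therefore an inference, though the natural one.
2. CT comes before ICA (section 8.1). Section 7.2.2 shows that CT findings are in use by then. It does not show that the coronary read reaches the operator.
3. The stated blinding is to clinical data and attaches to the stenosis readers. It cannot extend to the operator, whose verdict draws on clinical information by design.
4. The endpoint places the classification after the CT. That is a point in time; it does not require the classification to be recorded before the ICA. The protocol does not say who makes it.

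**Illustration of size**

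The protocol gives 30 patients without any expected accuracy or precision, so there is no stated figure to reproduce. Every input below is assumed: sensitivity 0.80, specificity 0.85 and prevalence p = 0.40. The 40% is the culprit-lesion rate that section 5.1 reports from an out-of-hospital arrest trial; this study also takes in-hospital arrests.

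- True accuracy: a = p × 0.80 + (1 − p) × 0.85. At p = 0.40, a = 0.32 + 0.51 = 0.83. At p = 0.20 and 0.60 it is 0.84 and 0.82.
- Random verdict error e: b = a(1 − e) + (1 − a)e. For e = 0, 0.05 and 0.10, b = 0.830, 0.797 and 0.764.
- Pull f is the share of discordant verdicts that follow the CT, and r is the share of that pull undone by intracoronary imaging: observed = b + f(1 − r)(1 − b).

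| e | r | f = 0.10 | f = 0.25 | f = 0.50 |
|---|---|---|---|---|
| 0 | 0 | 84.7% | 87.3% | 91.5% |
| 0 | 0.5 | 83.9% | 85.1% | 87.3% |
| 0.05 | 0 | 81.7% | 84.8% | 89.9% |
| 0.05 | 0.5 | 80.7% | 82.2% | 84.8% |
| 0.10 | 0 | 78.8% | 82.3% | 88.2% |
| 0.10 | 0.5 | 77.6% | 79.4% | 82.3% |

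With r = 1 the pull has no effect and the observed value is b.

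The net shift turns upward only when f exceeds (0.83 − b)/[(1 − b)(1 − r)]. For e = 0.05 that is 0.033/0.203 = 16%, or 33% if imaging undoes half the pull. For e = 0.10 it is 0.066/0.236 = 28%, or 56%.

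The extremes are 76.4 − 83 = −6.6 points (0.066 × 30 = 2.0 patients) with 10% error and no pull, and 91.5 − 83 = +8.5 points (0.085 × 30 = 2.6 patients) with 50% pull and no error. All these values lie inside the exact 95% interval for 25/30, 65.3% to 94.4%.

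The upper end depends on the assumed accuracy, because a less accurate test leaves more discordant cases. At a true accuracy of 70%, with no verdict error, a 50% pull would give 0.70 + 0.30 × 0.50 = 85%, or 4.5 of 30 patients.

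**The case against.** The strongest reply is that the point rests on silence and two inferences. The CCTA is not among the listed inputs to the verdict, and read order and locking may be set out in a SAP or reading manual not at hand. Intracoronary imaging gives direct lesion evidence in the doubtful cases. The primary objective is accuracy "by means of agreement with ICA", and that comparison has blinded paired readers. For a radiologist blinded to clinical data, the ICA result could reasonably count as clinical data. Finally, the study is small and descriptive, with no threshold that a shift could cross.

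Much of this stands as a limit on the claim. A reader might infer that the operator does see the CCTA read, or that the reported accuracy will be inflated. The documents support neither. The first is not stated anywhere, and the second does not follow, since random verdict error works in the opposite direction. Nor does the entry under section 7.4, that group allocation and blinding are not applicable, show that the operator is unmasked. It stands under a template heading in a non-randomised study that specifies reader blinding elsewhere.

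It does not remove the gap. Leaving the CCTA off a list of inputs is not masking. The operator decides when there is doubt, and obtains and interprets the intracoronary imaging. Agreement on stenosis does not settle cause: section 8.1 itself separates coronary disease with a culprit from disease without one. If the CT classification does come from the blinded CT readers, locking it is largely a matter of writing that down, but the protocol does not say that it does. Section 10.3 itself assigns the verdict to the operator, and whether the operator knew the CT result has to be recorded at the time. Lying inside the confidence interval is no comfort either, because the interval describes sampling error and makes no allowance for bias.

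**Conclusion.** The point holds as a gap in protection, not as a demonstrated bias. Following the protocol as written leaves the natural reference for the primary endpoint open to knowledge of the test it judges, while the stated safeguards cover only the stenosis grades. It rests on two inferences: that the operator's conclusion is the reference, and that the operator could know the CCTA coronary read. Neither the size nor the sign of any shift can be derived from the protocol; the figures above only show that a few patients out of 30 could be affected under assumed inputs.

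It should be fixed, with medium confidence. The remedy is cheap now and prespecified if made now, whereas a masked re-reading added after results are seen would be post hoc.

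**What to change.** In Protocol section 10.3:

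1. Name the reference for the primary endpoint.
2. State that the CCTA-based cause classification is recorded and locked without knowledge of the ICA result or the final cause.
3. Add a yes/no field for whether the operator knew the CCTA coronary result when giving the verdict.
4. Prespecify a second cause verdict by the ICA readers already planned, excluding the operator of that case, given after their stenosis grades are locked and without the CCTA coronary read. Report the percentage correctly classified against both verdicts.
5. Report separately the patients whose cause was settled by a non-coronary CT finding. For them the CT is part of both the index test and the reference, and masking the coronary read does not change that.

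Clinical use of the CT is unchanged.

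The cost is protocol wording, one data field and modest preparation of 30 case files. Where the operator is one of the planned readers, the third reader steps in, and a further reader may be needed if the two then disagree. Reported accuracy may come out lower. Some dependence on the operator remains, because the files will show the operator's choice of intracoronary imaging and PCI.

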11.1 Adverse Events

11.1.1 Definitions

An adverse event is any untoward medical occurrence, unintended disease or injury or any untoward clinical signs, including an abnormal laboratory finding, in subjects, users or other persons in the context of a clinical investigation, whether or not related to the investigational device.

Note:

- This definition includes events that are anticipated as well as unanticipated events
- This definition includes events occurring in the context of a clinical investigation related to the investigational device, the comparator or the procedures involved

11.1.2 Reporting

Adverse events will be reported based on the analysis of the clinical patient file.

11.1.3 Laboratory Test Abnormalities

Follow-up of renal function will be documented.

11.2 Serious Adverse Events

11.2.1 Definitions

Any adverse event that led to any of the following:

- Death,
- Serious deterioration in the health of the subject, that resulted in any of the following:

- Life-threatening illness or injury,
- Permanent impairment of a body structure or a body function,
- Hospitalization or prolongation of patient hospitalization,
- Medical or surgical intervention to prevent life-threatening illness or injury or permanent impairment of a body structure or a body function,
- Chronic disease

c) Foetal distress, foetal death or a congenital physical or mental impairment or birth defect.

Medical and scientific judgement should be exercised in deciding whether expedited reporting is appropriate in other situations, such as important medical events that may not be immediately life-threatening or result in death or hospitalisation but may jeopardise the patient or may require intervention to prevent one of the other outcomes listed in the definition above. These should also be considered serious.

11.2.2 *Immediate Reporting*

11.3 Suspected Unexpected Serious Adverse Reactions (SUSAR)

11.3.1 *Definitions*

An adverse reaction is any untoward medical occurrence in a patient or clinical investigation subject participating in a clinical trial including any abnormal sign, symptom, or disease temporally associated with the participant's involvement in the research, whether or not considered to be related to the research.

Serious if:

- Results in death,
- Is life-threatening,
- Requires inpatient hospitalization or prolongation of existing hospitalization,
- Results in persistent or significant disability/incapacity,
- Is a congenital anomaly/birth defect

Or

- Other important medical condition (ICH 2EA)

Medical and scientific judgement should be exercised in deciding whether expedited reporting is appropriate in other situations, such as important medical events that may not be immediately life-threatening or result in death or hospitalisation but may jeopardise the patient or may require intervention to prevent one of the other outcomes listed in the definition above. These should also be considered serious.

11.4 Device Deficiencies

11.4.1 *Definitions*

Any inadequacy in the identity, quality, durability, reliability, safety or performance of an investigational device, including malfunction, user errors or inadequacy in information supplied by the manufacturer.

12 Ethical Considerations

12.1 Ethical Conduct of the Study

12.1.1 *Declaration of Helsinki*

The trial will be performed in accordance with the Declaration of Helsinki, the conditions and principles of Good Clinical Practice, the protocol and applicable local regulatory requirements and laws.

12.1.2 *Ethics Committee*

Before the start of the trial or implementation of any amendment, approval of the trial protocol and amendments, informed consent forms and other relevant documents will be obtained from the applicable ethical committee(s).

12.2 Recruitment and Informed Consent

Recruitment will be done by the treating physician at the moment of ROSC after cardiac arrest. Each participant or his/her representative shall provide Informed Consent before performance of the ICA. The IC form that is/are used must be approved by reviewing EC and be in a language that the participant can read and understand. The ICF should be in accordance with current ICH and GCP guidelines and with applicable local regulations.

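### Consent is required only before the later, standard-of-care ICA, so the study-specific ECG-less CCTA may precede it and scanned patients can leave the feasibility denominator

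*Protocol*

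**What the plan says.** **Consent.** Section 12.2: "Each participant or his/her representative shall provide Informed Consent before performance of the ICA". The inclusion criterion in 7.2.1, repeated in the section 4 summary, reads "Informed consent from patient or representative obtained before invasive coronary angiography". No other consent deadline is given.

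**Screening and recruitment.** Section 8.1.1: "Screening will be performed by the treating physician in every cardiac arrest patient at the moment of ROSC". Section 12.2: "Recruitment will be done by the treating physician at the moment of ROSC after cardiac arrest". Neither sentence requires consent at that moment.

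**Order and status of the imaging.** The schedule in 8.1 opens with "Chest CT scan (as early as possible) + CT brain" and the ECG-less CCTA in the same row. The ICA follows within 24 hours of the CT and is labelled standard of care. The CT row carries both labels, standard of care and study-specific.

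**Feasibility.** The study parameters in 8.1 define it as "Feasibility (patients meeting inclusion criteria where ECG-less CCTA with sufficient quality was obtained". Feasibility is named in the primary objective (6.1) and is a secondary endpoint (6.3).

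**Ethics.** Section 12.1: "The trial will be performed in accordance with the Declaration of Helsinki, the conditions and principles of Good Clinical Practice". The same section requires ethics committee approval of the protocol and consent forms.

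**The concern.** The consent requirement is attached to the procedure that the protocol treats as routine, not to the one done for research. Two consequences follow.

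First, a patient can receive the study scan, with its added radiation, before anyone has consented. The protocol does not say on what basis, or what happens to the data if consent is later refused or never obtained.

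Second, whether a scanned patient meets the inclusion criteria can be settled after the images exist. Since feasibility is counted only among patients who meet those criteria, its denominator can depend on events after the scan. With a target of 30 patients, a few uncounted scans would move the percentage visibly, and the report would not show that they were missing.

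**Working it through.** The point rests on the order of events. The protocol gives no feasibility target or precision, so there is no planned figure to reproduce.

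**1. Sequence**

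| Step | Timing | Status | Consent required by then? |
|---|---|---|---|
| Screening, recruitment (8.1.1, 12.2) | at ROSC | – | no |
| Conventional CT (8.1) | as early as possible | standard of care | no |
| ECG-less CCTA (8.1) | same session and contrast bolus | study-specific | no |
| ICA (8.1) | under 24 h after CT | standard of care | yes |

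The two labels in the CT row do not line up with its items in the extracted text. The assignment is still clear: section 5.1 describes head and chest CT as general practice in these patients, and 8.1 describes the ECG-less scan as added examination time with its own dose.

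**2. Added exposure (8.1, 9.2).** The average DLP is 150 to 200 mGy.cm against a cited reference level of 300: 150/300 = 50% and 200/300 = 67%. No contrast is added, and the examination lengthens by about one to two minutes.

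**3. Who leaves the denominator.** The inclusion criteria contain consent before ICA. A scanned patient fails that criterion if no consent is given before the ICA, whether through death, refusal, no representative reached in time, or because no ICA takes place and consent was not sought. Read literally, 8.1 then leaves this patient out of feasibility. The log in 12.4 covers participants, not attempted scans. Section 7.4 gives blinding as not applicable. The reader blinding in 8.1 and 10.3 concerns clinical data, so nothing keeps whoever seeks consent unaware of the scan.

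**4. Possible size (assumed inputs).** Let f be the true share of adequate scans, and r the chance of enrolment after a failed scan relative to a successful one.

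Apparent feasibility = f / (f + (1 − f) × r)

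| f | r | Calculation | Apparent |
|---|---|---|---|
| 0.80 | 1 | 0.80/1.00 | 80.0% |
| 0.80 | 0.75 | 0.80/0.95 | 84.2% |
| 0.80 | 0.50 | 0.80/0.90 | 88.9% |
| 0.80 | 0.25 | 0.80/0.85 | 94.1% |
| 0.80 | 0 | 0.80/0.80 | 100% |
| 0.70 | 0.50 | 0.70/0.85 | 82.4% |
| 0.90 | 0.50 | 0.90/0.95 | 94.7% |

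If successful scans were lost more often, the bias would reverse. With f = 0.80 and r = 1.25, the result is 0.80/1.05 = 76.2%.

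**5. The same in counts (assumed).** Suppose 27 of 30 enrolled patients have adequate scans (90%) and 8 more were scanned but not consented. Over all 38 scans, feasibility is 35/38 = 92.1% if none of the 8 failed, 31/38 = 81.6% if 4 failed, and 27/38 = 71.1% if all failed. The exact 95% interval for 27/30 is 73.5% to 97.9%.

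**The case against.** Several objections carry weight.

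- **Before the ICA is a latest time.** A reader might infer that patients are always scanned before consent. The documents do not say so. Recruitment is placed at ROSC, and consent may be obtained before the CT. What stands is that nothing requires it then, and that in newly resuscitated patients with a CT as early as possible it may often be impracticable.
- **No breach is shown.** A reader might infer that the protocol contradicts its own commitment in 12.1. That section cites the Declaration of Helsinki, GCP and local law but quotes no rule on emergency consent, and it sends the protocol to an ethics committee. The supported statement is that the basis for scanning before consent is not given.
- **Failed scans are of interest to the study.** It is tempting to conclude that they would go unconsented and that feasibility is therefore inflated. Yet 6.3 makes the reasons for failed CCTA reporting an endpoint, which is a reason to enrol them. Selective consent is possible, not shown.
- **The primary endpoint.** A reader might infer that its case mix is distorted. Patients without ICA lack the reference assessment in 10.3 and could not contribute under any consent rule. That others are hurried to ICA and lost before consent is conjecture.
- **The figures are assumed.** The 81.6% scenario lies within sampling error of 27/30, and 71.1% needs every uncounted scan to fail. This is fair, but an exact interval shows sampling error and does not show selection.
- **Enrolment at the decision to scan** would collide with the exclusion in 7.2.2 for CT findings that rule out early angiography, which is known only afterwards. This is correct, and the fix has to deal with it.

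**Conclusion.** The concern holds in a limited form. The protocol permits the study-specific CCTA before consent and states no emergency or deferred basis for it. Its feasibility definition, read literally, omits scanned patients who die, refuse, have no ICA or are not consented in time, and this can be decided after the scan outcome is known.

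The first part follows directly from sections 4, 7.2.1, 8.1 and 12.2. The second rests on reading the denominator in 8.1 as written. The amount and direction of any bias are unknown. At an assumed true feasibility of 80%, the apparent figure runs from 84.2% to 100% as r falls from 0.75 to 0, and it falls below 80% if r exceeds 1. Feasibility is part of the primary objective, so its denominator should not be left open to this. Neither an effect on the primary endpoint nor a breach of 12.1 is established.

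**What to change.** 1. In 7.2.1 and 12.2 (and the section 4 summary), tie consent to the ECG-less CCTA, or state the ethics-committee-approved deferred-consent procedure that covers it. Under either, consent is sought regardless of scan quality, scan result or whether an ICA is done.
2. Log every patient in whom the ECG-less acquisition is started, and use that log as the feasibility denominator in 8.1. Where consent is refused, keep anonymous counts as far as ethics and data-protection rules allow.
3. Apply the exclusion for CT findings that preclude angiography, and the need for an ICA, only to the CCTA–ICA agreement and classification analyses, not to feasibility. This removes the conflict with an exclusion that is known only after the CT.

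Where deferred consent is the usual route, consent will still follow the scan. The gain is then a stated basis and a denominator that does not depend on consent.

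The cost is a protocol and consent-form amendment with ethics approval, a scan log, and possibly a lower feasibility figure. The change is best made before patients are scanned, because a count of started scans is hard to rebuild later.
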